### 4. STUDY DESIGN AND ENDPOINTS

#### 4.1 DESCRIPTION OF THE STUDY DESIGN

This study is a prospective, single-arm clinical study to be conducted at up to three clinical sites in the US. Up to 10 subjects will be enrolled and treated if they meet the inclusion/exclusion criteria and provide written informed consent.

Enrolled subjects meeting all entrance criteria and confirmed eligible for study treatment will be asked to participate. Subjects will receive a lower facelift surgery per the Investigator's standard clinical practice and treatment with the Renuvion APR System. The mid/upper-face area will not be treated with Renuvion and the lower face/neck area will be treated with Renuvion. Treatment will consist of subdermal coagulation of soft tissue using the Renuvion APR handpiece.

Standardized images will be taken prior to treatment and during each follow-up visit using the site's camera system. Baseline assessments and pre-treatment images should be obtained within 30 days of the study treatment.

 Apyx Medical Corporation	
Protocol Number: APX-21-04	Effective Date: March 19, 2024 Revision No: 7.0
Title: Histological Evaluation of Human Skin Biopsies to Assess the Effects of Renuvion APR Treatment as an Adjunct Procedure in Facelift Surgery	

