## 4.3 STUDY OUTCOME MEASURES

1. Change in histology evaluation of biopsy tissue between the untreated portion of the face and the Renuvion treated portion at the D180 visit and compared to baseline.
2. Analysis of all adverse events through the D180 follow-up visit.
3. Analysis of bruising post-procedure.
4. Analysis of swelling post-procedure.
5. Healing profile.
6. Analysis of bleeding during surgery.
7. The Principal Investigator will complete a PGAIS assessing overall aesthetic improvement in the treatment area at day 45, 90, and 180 post-treatment.
8. The subject will complete a SGAIS assessing overall aesthetic improvement in the treatment area at day 45, 90, and 180 post-treatment.
9. The subject will complete a Patient Satisfaction Questionnaire (PSQ) at the 180-day follow-up visit.
10. Change in estimated biological skin age from baseline to D180.

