#### 4.3.4.1 HISTOLOGY EVALUATION OF BIOPSY TISSUE

Tissue samples will be assessed via microscopy, histology, and immunohistochemistry for biological markers of elasticity (collagen density, elastin, fibrillin-1) and hydration (HA) at Baseline and Day 180.

[figure not shown]
The density of dermal collagen is an indicator of skin elasticity because of collagen's role in maintaining the strength of the skin, helping it to resist mechanical deformation. Other biological markers of elasticity are fibrillin-1, a glycoprotein that supports the integrity of the dermal elastic fiber network, and elastin, an essential protein of the elastic fibers of the skin, such as oxytalan and elaunin. Well-studied biological markers of skin hydration include aquaporin-3 (AQP3), water- and glycerol-transporting membrane proteins expressed in the epidermis and glycosaminoglycans (GAGs), which are linear polysaccharide molecules, including HA, that bind water and help regulate the hydration of the dermis.

Two living human skin tissue samples will be collected at baseline during the facelift procedure prior to any treatment with the Renuvion APR system and at Day 180 post-surgery (D180) during the follow up visit. Skin punch biopsies ranging from 3-5 mm in diameter will be obtained from left side of the face. One tissue sample will be taken from the untreated portion of the face within 2cm of the Root of the Helix and 2cm of the hairline. Measures should be taken to ensure the biopsy is taken from facial skin, rather than scalp skin. The second tissue sample will be obtained from cheek skin in the untreated area of the lower face within 2 cm of the treatment line. See **Figure 3**. Both biopsies will be taken prior to any treatment with the Renuvion APR System at Baseline and then again after treatment at the same locations at D180. The untreated skin tissue samples from non-surgical sites for each subject will be provided as control specimen. The tissue samples will be fixed in 10% neutral buffered formalin and prepared for histological and immunohistochemical assessments. In brief, tissues will be gross-trimmed, dehydrated, oriented

 Apyx Medical Corporation	
Protocol Number: APX-21-04	Effective Date: March 19, 2024 Revision No: 7.0
Title: Histological Evaluation of Human Skin Biopsies to Assess the Effects of Renuvion APR Treatment as an Adjunct Procedure in Facelift Surgery	

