and embedded in paraffin, and histology slides of sectioned tissue at 3-5 mm will be prepared. All slides will be stained for hematoxylin and eosin (H&E), trichrome, Verhoeff Van 21Gieson stain. Expression of biological markers will be assessed by immunohistochemistry (IHC) at two timepoints. The collected samples at baseline and D180 will be stained for elastin and fibrillin-1. Histopathological evaluation and the integrity of the dermal elastin and collagen fibers will be assessed and semi-quantitatively scored via light microscopy by a board-certified pathologist. Additional staining may be needed at the discretion of the pathologist.

FIGURE 3: BIOPSY LOCATIONS

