### 7.3.2 POST-PROCEDURE CARE INSTRUCTIONS

Subjects will be asked to return to the study site at the following times post-procedure:

- 1 day
- 2(+1) days (optional)
- 7 (±3) days

Apyx Medical Corporation

Protocol Number: APX-21-04

Effective Date: March 19, 2024

Revision No: 7.0

Title: Histological Evaluation of Human Skin Biopsies to Assess the Effects of Renuvion APR Treatment as an Adjunct Procedure in Facelift Surgery

- 14 ( $\pm 3$ ) days
- 45 ( $\pm 7$ ) days
- 90 ( $\pm 10$ ) days
- 180 ( $\pm 15$ ) days

Post-procedure assessments and 2D photographic imaging will be performed during the follow-up visits. The same standardized photography views will be used throughout the study.

Due to the challenges of COVID-19, if a subject is unable to return to the office for an in-person visit, follow-up visits will be conducted virtually. If a visit is completed virtually, missing assessments such as photographs will be documented as a protocol deviation specifically noting COVID-19. Outside of photographs, study investigators and study staff will ensure all other assessments related to each follow-up visit are completed virtually if the visit is done virtually. For virtual visits, the investigator and/or study staff completing the visit and assessments will be identified on the case report form; as well, the manner in which the visit was completed will also be recorded (i.e. video call, phone call, etc.). Virtual visits should be done via video call if possible, to ensure subject identity. If a telephone call must be done, the investigator and/or study staff must positively identify the subject prior to conducting the virtual visit by requesting the subject to state their address and date of birth. Subjects will be strongly encouraged to come in (albeit safely) for their D180 visit; this visit is vitally important as this is the primary endpoint and photographic images are needed for many of the assessments. Only investigators and study staff who have been trained and delegated to conduct virtual visits as indicated on the delegation log may conduct virtual study visits.

Subjects may be seen for an unscheduled appointment at any time at investigator's discretion.

Apyx Medical Corporation

Protocol Number: APX-21-04

Effective Date: March 19, 2024

Revision No: 7.0

Title: Histological Evaluation of Human Skin Biopsies to Assess the Effects of Renuvion APR Treatment as an Adjunct Procedure in Facelift Surgery

TABLE 3: STUDY REQUIRED PROCEDURES

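### The leading histology outcome is a reader-dependent score, and the protocol specifies no masking, slide coding, reading order or shared staining run

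*Combined protocol and SAP*

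**What the plan says.** Section 4.3 lists ten outcomes. The first is "Change in histology evaluation of biopsy tissue between the untreated portion of the face and the Renuvion treated portion at the D180 visit", with a further comparison to baseline. No outcome is formally named primary, but Section 7.3.2 says of the Day 180 visit that "this visit is vitally important as this is the primary endpoint". Histology is therefore fairly read as the leading outcome.

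Section 4.3.4.1 describes two biopsy sites on one side of the face, sampled "prior to any treatment with the Renuvion APR System at Baseline and then again after treatment at the same locations at D180". One site serves as the internal control: "The untreated skin tissue samples from non-surgical sites for each subject will be provided as control specimen". Fibre integrity is "assessed and semi-quantitatively scored via light microscopy by a board-certified pathologist". On staining, the section says "Expression of biological markers will be assessed by immunohistochemistry (IHC) at two timepoints" and "The collected samples at baseline and D180 will be stained for elastin and fibrillin-1". It gives no scale, grade definitions, masking, slide code, reading order, second reader or rule on which samples share a staining run.

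Section 4.1 states: "This study is a prospective, single-arm clinical study". Section 10.1 plans descriptive statistics only, Section 10.2 caps the study at 10 treated subjects, and Section 5.5.2 rules out replacing withdrawals.

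**The concern.** A semi-quantitative score read by eye depends on the reader. If the pathologist can tell that a slide is the treated site at Day 180, the expectation of improvement can move the score. Staining intensity and a reader's own grading can also shift over months, and the two visits are 165 to 195 days apart under the Table 3 window. Nothing in the plan prevents baseline slides from being stained and read well before Day 180 slides.

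There is no untreated group of subjects, so protection against a spurious improvement has to come from the untreated skin site and from how slides are handled. The plan supplies the untreated site but is silent on slide handling.

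**Working it through.** **Plan's own figure.** There is none to reproduce. Section 10.2 gives a cap of 10 without effect size, SD, alpha or power.

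**Search for a safeguard.** The only mention of double-blinding is in the title of a cited filler trial. The abbreviation list includes an independent photographic reviewer, but no procedure uses one, and it would concern photographs. The only slide labelling described is that untreated samples are supplied as controls.

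**Which comparisons are exposed.** Two sites by two visits give four samples per subject. Call the lower-face site T and the untreated upper site C, and let b be the bias added to a slide's score. I take the Day 180 lower-face sample as treated, as the first outcome requires. Section 4.3.4.1 describes that site as lying in untreated skin near the treatment line, and the two passages need to be reconciled.

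- Before-after change at T: b(T, D180) − b(T, baseline)
- Day 180 contrast: b(T, D180) − b(C, D180)
- Difference in change: [b(T, D180) − b(T, baseline)] − [b(C, D180) − b(C, baseline)]

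With an assumed shift of 0.5 score units and no true effect:

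| Source of shift | Before-after at T | Day 180 T − C | Difference in change |
|---|---|---|---|
| Drift at D180 shared by both sites | 0.5 | 0.5 − 0.5 = 0 | 0.5 − 0.5 = 0 |
| Drift at D180 on T only (sites in different runs) | 0.5 | 0.5 | 0.5 |
| Reader expectation on the treated D180 slide | 0.5 | 0.5 | 0.5 |
| Shared drift plus reader expectation | 1.0 | 1.0 − 0.5 = 0.5 | 1.0 − 0.5 = 0.5 |

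The untreated site removes shared additive drift. It does not remove expectation attached to the treated slide.

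**Scale of the problem, for illustration.** The documents give no score range or SD, so bias is expressed in SDs of the paired change. All bias sizes are assumptions, and the score is treated as roughly normal.

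- Half-width of a 95% interval for the mean paired change = t(0.975, n−1)/√n. At n = 10: 2.262/3.162 = 0.72 SD. At n = 8 (assuming two incomplete sets): 2.365/2.828 = 0.84 SD.
- Probability that the interval excludes zero with no true effect = 1 − F(t; n−1, δ) + F(−t; n−1, δ), where t is the quantile above, F is the noncentral t distribution function and δ = bias × √n.
- n = 10: bias 0.25 gives δ = 0.791 and 10.9%; bias 0.5 gives δ = 1.581 and 29.3%.
- n = 8: bias 0.25 gives δ = 0.707 and 9.4%; bias 0.5 gives δ = 1.414 and 23.2%.

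The nominal value without bias is 5%.

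**The case against.** Four counter-arguments deserve a hearing.

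**Silence is not open reading.** A reader might infer that slides will be read unmasked. The documents do not say so, and a laboratory procedure outside the protocol may provide masking. This stands: only the omission is established.

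**The untreated site already controls drift.** A reader might infer that drift is wholly confounded with time. It is in the simple before-after change, but the first part of the first outcome is a treated-untreated contrast at Day 180, where shared additive drift cancels. This stands in part. The comparison with baseline is also a stated outcome, a shared run is not guaranteed, and the plan does not name the difference in change as a summary. Expectation about the treated slide survives in every contrast.

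**The immunohistochemistry sentence is weak evidence.** The two timepoints could be taken to mean two staining sessions. The following sentence, on staining the baseline and Day 180 samples, makes biopsy visits the more natural meaning. The text allows separate staining but does not prescribe it.

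**The analysis is descriptive.** No test or interval is planned, so the percentages describe no planned analysis. That limits their meaning. It does not remove the bias, which a reported mean carries just as an interval does.

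Nor is histology the only outcome that could be masked. The GAIS in Section 4.3.4.2 has a photograph-comparison step that a masked reviewer could perform, and the methylation age in Section 4.3.4.8 comes from an array and algorithm rather than from the pathologist's score.

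**Conclusion.** The point holds as an uncontrolled risk on paper. The leading outcome depends on a reader's score, and the protocol specifies none of the usual safeguards for reading or staining. Reader expectation about the treated Day 180 slide would enter all three comparisons in full. Drift between visits would enter the before-after change, and would cancel against untreated skin only if it is additive and both sites share a run.

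The size of either bias cannot be computed from the documents. The range of about 11% to 29% rests on an assumed bias of 0.25 to 0.5 SD, complete data on 10 subjects and a roughly normal change. It must not be read as this study's false-positive rate. The score as written covers histopathology and elastin and collagen fibre integrity; how the other markers are quantified is not stated.

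This is a safeguard the sponsor should add. It does not show that the results will be wrong. Masking also cannot separate the facelift's effect from the device's, because Section 4.3.4.1 describes the control samples as coming from non-surgical sites.

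**What to change.** Add to Section 4.3.4.1:

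*Each subject's blocks are held until that subject's D180 biopsy; all four samples are sectioned and stained in the same run. Slides carry a random code and are read in random order by the same pathologist, masked to subject, visit and site until scores are locked.*

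Report the treated-minus-untreated difference in change alongside the before-after change. If a laboratory procedure already covers masking and batching, a sentence citing it would suffice. If baseline slides have already been stained, cut new sections where tissue remains, or at least re-read the existing slides coded.

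The samples are fixed in formalin and embedded in paraffin, so waiting is feasible. Holding blocks only to the subject's own Day 180 visit is enough, because every comparison is within subject; holding all blocks to the last subject's visit would add delay without need.

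Costs: slide coding, no early baseline histology, and later transfer of leftover tissue for the methylation analysis in Section 4.3.4.8. No extra subject, visit, biopsy or reader is needed. Masking may be imperfect, since follicle pattern may reveal the site and scarring from the earlier punch or the surgery may reveal the visit.

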#### 4.3.4.2 GLOBAL AESTHETIC IMPROVEMENT SCALE (GAIS)

The Global Aesthetic Improvement Scale (GAIS) is a 5-point scale that rates global aesthetic improvement from the pretreatment appearance. In this study, both live observation and photo review are utilized by the physician or a qualified, delegated clinician and subject in order to assign a score. The PGAIS must be performed by the principal investigator, sub-investigator or qualified clinician delegated by the principal investigator. Both the PGAIS and SG AIS should be completed in two steps:

- Based on a live assessment of the subject while referring to the subject's pre-treatment photographs (subjects should be given a hand mirror for assessment); and
- Based on a comparison of the subject's pre-treatment photographs to the current post-treatment photographs.

The Investigator will grade the overall improvement of treatment area as indicated in **Table 3** by comparing the subject's appearance at follow-up visits against a photograph taken prior to procedure. Likewise, the subject will also rate their improvement compared to pre-treatment as shown in **Table 4**. The GAIS results will be collected at the 45-day, 90-day and 180-day follow-up visits.

 APYXTM MEDICAL Apyx Medical Corporation	
Protocol Number: APX-21-04	Effective Date: March 19, 2024 Revision No: 7.0
Title: Histological Evaluation of Human Skin Biopsies to Assess the Effects of Renuvion APR Treatment as an Adjunct Procedure in Facelift Surgery	

**TABLE 2.1: GLOBAL AESTHETIC IMPROVEMENT SCALE EVALUATION - INVESTIGATOR**

Rating	Description
Very much improved	Optimal cosmetic result from this procedure in this subject
Much improved	Marked improvement in appearance from the initial condition, but not completely optimal for this subject
Improved	Obvious improvement in appearance from the initial condition
No change	The appearance is essentially the same as the original condition
Worse	The appearance is worse than the original condition
Much worse	The appearance is much worse than the original condition
Very much worse	The appearance is very much worse than the original condition

**TABLE 2.2: GLOBAL AESTHETIC IMPROVEMENT SCALE EVALUATION - SUBJECT**

Rating	
Very much improved	
Much improved	
Improved	
No change	
Worse	
Much worse	
Very much worse	

#### 4.3.4.3 PATIENT SATISFACTION QUESTIONNAIRE (PSQ)

The study subjects will be asked to complete a Patient Satisfaction Survey, see **Appendix A**, at the 180-day follow-up visit.

#### 4.3.4.4 ADVERSE EVENT REPORTING

The definitions of Adverse Events (AEs) and the subtypes are provided in **Section 8** of the study protocol. Adverse events will be classified by the investigator as to:

- Anticipated vs unanticipated.
- Serious vs not serious.
- Expected Treatment Effect (ETE) vs Adverse Event (AE).
- Severity: mild, moderate, severe.
- Device causality: not related, related, undetermined.
- Procedure causality: not related, related, undetermined.

Apyx Medical Corporation

Protocol Number: APX-21-04

Effective Date: March 19, 2024

Revision No: 7.0

Title: Histological Evaluation of Human Skin Biopsies to Assess the Effects of Renuvion APR Treatment as an Adjunct Procedure in Facelift Surgery

#### 4.3.4.5 2D PHOTOGRAPHY

2D Images will be captured at baseline and follow-up visits on Days 45, 90, and 180 as per typically captured in the sites' practice. Images will be uploaded to Dropbox for transfer to the sponsor.

#### 4.3.4.6 HEALING PROFILE

The study investigator will document the healing progress at all follow-up visits on study-specific CRFs.

#### 4.3.4.7 ASA PHYSICAL STATUS CLASSIFICATION SYSTEM

The ASA Physical Status Classification System has been in use for over 60 years. The purpose of the system is to assess and communicate a patient's pre-anesthesia medical co-morbidities. The classification system alone does not predict the perioperative risks, but used with other factors (e.g., type of surgery, frailty, level of deconditioning), it can be helpful in predicting perioperative risks, see **Table 5**.

TABLE 2: ASA PS CLASSIFICATION

ASA PS Classification	Definition	Adult Examples, Including, but not Limited to:
ASA I	A normal healthy patient	Healthy, nonsmoking, no or minimal alcohol use.
ASA II	A patient with mild systemic disease	Mild diseases only without substantive functional limitations. Current smoker, social alcohol drinker, pregnancy, obesity (30<BMI<40), well-controlled DM/HTN, mild lung disease.
ASA III	A patient with severe systemic disease	Substantive functional limitations; One or more moderate to severe diseases. Poorly controlled DM or HTN, COPD, morbid obesity (BMI ≥40), active hepatitis, alcohol dependence or abuse, implanted pacemaker, moderate reduction of ejection fraction, ESRD undergoing regularly scheduled dialysis, history (>3 months) of MI, CVA, TIA, or CAD/stents.
ASA IV	A patient with severe systemic disease that is a constant threat to life	Recent (<3 months) MI, CVA, TIA or CAD/stents, ongoing cardiac ischemia or severe valve dysfunction, severe reduction of ejection fraction, shock, sepsis, DIC, ARD or ESRD not undergoing regularly scheduled dialysis.
ASA V	A moribund patient who is not expected to survive without the operation	Ruptured abdominal/thoracic aneurysm, massive trauma, intracranial bleed with mass effect, ischemic bowel in the face of significant cardiac pathology or multiple organ/system dysfunction.
ASA VI	A declared braindead patient whose organs	(Intentionally left blank)

#### 4.3.4.8 DNA METHYLATION

Tissue samples at baseline and at D180 will be assessed for a skin-specific age predictor (DNA methylation analysis).

DNA methylation (DNAm) is a process that undergoes predictable age-dependent modifications. A highly accurate skin-specific age algorithm will analyze these modifications related to human skin health and molecular aging – quantifying the skin health/skin age of the tissue beyond the chronological age of the subject. Hallmarks of aging include genomic instability, telomere attrition, epigenetic alterations, loss of proteostasis, deregulated nutrient sensing, mitochondrial dysfunction, cellular senescence, stem cell exhaustion, and altered intercellular communication.

When available, biopsy tissue remaining after assessments via microscopy, histology, and immunohistochemistry for biological markers of elasticity (collagen density, elastin, fibrillin-1) and hydration (HA) will be transferred to the University of Miami and then processed using the Illumina Human Methylation EPICv2 array for DNAm data. These data will be analyzed to determine if Renuvion treatment is able to reverse or improve DNAm age.

Apyx Medical Corporation

Protocol Number: APX-21-04

Effective Date: March 19, 2024

Revision No: 7.0

Title: Histological Evaluation of Human Skin Biopsies to Assess the Effects of Renuvion APR Treatment as an Adjunct Procedure in Facelift Surgery

Any remaining tissue sample following the DNAm analysis will be destroyed.

## 5. SUBJECT ENROLLMENT AND WITHDRAWAL

### 5.1 STUDY POPULATION

The study population will consist of males and females between 18 and 75 years of age who have chosen to participate in this clinical trial as evidenced by execution of the informed consent document and meet eligibility criteria defined in this protocol are eligible for participation in this clinical trial. Subjects will be considered enrolled into the study when they have signed an approved informed consent form. Subjects who are enrolled and do not meet eligibility criteria will be exited as a screen fail without study treatment. A study exit Case Report Form will be completed for all enrolled subjects.

